5.3.1.2 Assessment of Pain and Overall Assessment of Disease Activity

The following assessments will be performed on the scheduled assessment days from the baseline:

- (1) Subject's assessment of pain: The subject assesses his/her own pain severity on a VAS of 0–100 mm on the questionnaire form. The measured value and the date of assessment will be entered in the eCRF.
- (2) SGA: The subject assesses his/her own disease activity on a VAS of 0–100 mm on the questionnaire form. The measured value and the date of assessment will be entered in the eCRF.
- (3) PGA: The investigator/sub-investigator assesses the subject's disease activity on a VAS of 0–100 mm on the physician assessment table. The measured value and the date of assessment will be entered in the eCRF.

5.3.1.3 Acute Phase Reactants (CRP and ESR)

Only CRP is measured during the screening test period. Blood sampling is performed on the scheduled assessment days from baseline to measure CRP and ESR. The measurement of CRP will be performed by the central laboratory, and the measurement of ESR will be performed by each study center. These results will be used to calculate DAS28, SDAI, and ACR response criteria assessment. One-hour value of ESR will be measured. The measured ESR and the date of measurement will be entered in the eCRF.

5.3.1.4 EULAR Response Criteria

Based on DAS28 scores and changes in DAS28 scores before and after treatment with the study drug or reference drug, EULAR Response Criteria categorize response to treatment as “No response,” “Moderate response,” or “Good response” according to the definition given in the table below [van Gestel et al, 1996; van Gestel et al, 1998].

- CONFIDENTIAL -

Table Definition of EULAR Response Criteria Assessment

DAS28 after treatment	DAS28 response (DAS28 before treatment - DAS28 after treatment)		
	> 1.2	> 0.6 and ≤ 1.2	≤ 0.6
≤ 3.2	Good response	Moderate response	No response
> 3.2 and ≤ 5.1	Moderate response	Moderate response	No response
> 5.1	Moderate response	No response	No response

5.3.1.5 DAS28

The subject's DAS28 will be calculated at the screening visit and on each subsequent assessment day using data from the following assessments, together with the formula shown below [Prevoo et al, 1995; van der Heijde et al, 1990; Fransen et al, 2003; Mallya et al, 1982; Wolfe, 1997].

- TJC (28 joints)
- SJC (28 joints)
- CRP or ESR
- SGA

[When CRP is used]

$$\text{DAS28} = 0.56\sqrt{\text{TJC}} + 0.28\sqrt{\text{SJC}} + 0.36 \ln(\text{CRP} + 1) + 0.014 \times \text{SGA} + 0.96$$

[When ESR is used]

$$\text{DAS28} = 0.56\sqrt{\text{TJC}} + 0.28\sqrt{\text{SJC}} + 0.70 \ln \text{ESR} + 0.014 \times \text{SGA}$$

DAS28 score is assessed as below.

- High disease activity: DAS28 score of > 5.1
- Moderate disease activity: DAS28 score of > 3.2 and ≤ 5.1
- Low disease activity: DAS28 score of ≤ 3.2

If the DAS28 score is less than 2.6, the subject will be considered to be in DAS28 remission [van Gestel et al, 1998; Fransen and van Riel, 2005].

5.3.1.6 SDAI Score

The SDAI score at baseline and Week 12 will be calculated using data from the following assessments, together with formula shown below [Smolen et al, 2003; Aletaha and Smolen, 2005; Felson et al, 2011].

- TJC (28 joints)
- SJC (28 joints)
- SGA
- PGA
- CRP (mg/dL)

$$\text{SDAI} = \text{TJC} + \text{SJC} + \text{SGA} + \text{PGA} + \text{CRP}$$

The SDAI score is assessed as below.

- High disease activity: SDAI score exceeding 26
- Moderate disease activity: SDAI score exceeding 11 and not greater than 26

- CONFIDENTIAL -

- Low disease activity: SDAI score exceeding 3.3 and not greater than 11

If the SDAI score is 3.3 or less, the subject will be considered to be in SDAI remission.

5.3.1.7 ACR Response Criteria Assessment

ACR Response Criteria [Felson et al, 1995] measure improvement in TJC, SJC, subject's assessment of pain, SGA, PGA, assessment of physical function using HAQ-DI, and acute phase reactant (CRP or ESR).

The ACR20 response requires that all criteria from (1) to (3) below be met. The ACR50 response indicates a 50% improvement in all criteria from (1) to (3) below, and the ACR70 response similarly indicates a 70% improvement. In this study, [5] is assessed with CRP.

- (1) TJC: $\geq 20\%$ reduction compared with baseline
- (2) SJC: $\geq 20\%$ reduction compared with baseline
- (3) $\geq 20\%$ improvement in 3 or more of the following 5 parameters compared with baseline

[1] Subject's assessment of pain

[2] SGA

[3] PGA

[4] Disability Index (HAQ-DI)

[5] CRP or ESR

5.3.1.8 Patient Reported Outcomes/Assessments

Subjects will complete the following assessments at baseline and on days specified in the Schedule of Assessments. The outcome of the assessments will be recorded in the eCRF. In principle, the copy of assessment forms will be provided to the sponsor.

- HAQ-DI [Fries et al, 1982; Ramey et al, 1992]
- SF-36v2[®] [Ware, 2004]
- WPAI [Takeuchi T, 2011; Reilly MC, 1993]

5.3.2 Pharmacodynamic Assessments

Blood samples will be collected at baseline and on days specified in the Schedule of Assessments. At the study visit points where blood sample collection for PK assessment is performed, sample collection for PD assessment will be performed before treatment with the study drug or reference drug and at the same time as that for the sampling for PK assessment. These measurements will be performed at the central laboratory, and the results will be reported to the sponsor and the study center after the breaking of the treatment code.

5.3.2.1 Lymphocyte Subsets

Lymphocyte subset quantification of CD3, CD4, CD8, CD16, CD19, CD56, and CD56/16 will be performed, and the changes from baseline will be calculated. The date of blood sampling will be entered in the eCRF.

- CONFIDENTIAL -

5.3.2.2 Biomarkers for Efficacy and Safety Assessments

To assess the effects of ASP015K on biomarkers, VEGF and MMP-3 will be measured, and the changes from baseline will be calculated. The date of blood sampling will be entered in the eCRF.

Additional analysis may be performed for biomarkers for efficacy and safety assessments based on study results using blood samples that have been collected during the study and biobanked (i.e., residual sample stored for retrospective analysis). These could include biomarkers of inflammation, bone or cartilage metabolism, or inhibitory activity of JAK, but other biomarkers may also be subject to analysis.

5.3.3 Pharmacokinetic Assessments

The concentration of ASP015K will be measured. If necessary, the concentrations of ASP015K metabolites will also be measured. Subjects in the reference group will be excluded from concentration measurement and will not provide blood samples. Blood samples will be collected at baseline and on the days specified in the Schedule of Assessments. Moreover, the date and time on which the last dose of study drug will be taken just prior to blood sampling will be recorded in the eCRF, together with the date and time of blood sampling.

The sampling for the assessment of post-dose concentrations will be performed as a substudy at study centers approved for the sampling. The sampling for the assessment of post-dose concentrations will be performed at either Week 4 or Week 8, 2 hours after the administration of the study drug (the acceptable time range is from 1 hour to 4 hours post-dose). In addition, the sampling for post-dose concentrations will be performed on the same day as central ECG at Week 4 or Week 8, promptly after the central ECG.

5.4 Safety Assessment

The following tests and observations will be made for the purpose of safety assessments at baseline and on the days specified in the Schedule of Assessments. The requirements for reporting and analysis of information on drug-induced liver injury (DILI) are in Appendix 4 "Liver Safety Monitoring and Assessment." If marked liver function abnormal in Appendix 4 is observed, the investigator or the responsible personnel should contact the sponsor or CRO by telephone or fax (within 24 hours of awareness).

5.4.1 Vital Signs

Blood pressure (in the sitting position), pulse rate, and body temperature at rest will be measured at screening and on the days specified in the Schedule of Assessments. The date of measuring and measurements taken (blood pressure and the measuring position, systolic blood pressure, diastolic blood pressure, pulse rate, and body temperature) will be entered in the eCRF.

- CONFIDENTIAL -

5.4.2 Body Weight

Body weight will be measured at screening and on the days specified in the Schedule of Assessments. The date of measuring and measurements taken will be entered in the eCRF.

5.4.3 Adverse Events

The survey period for AEs will be from the initiation of treatment with the study drug or reference drug to before the initiation of administration in the extension study or until the end of follow-up.

Events that occurred after treatment with the study drug or reference drug until before the initiation of administration in the extension study or until the end of follow-up will be recorded as AEs. Concurrent diseases that worsened during the study will also be recorded as AEs. AEs that occurred after the subject has completed the study plan or has been discharged from the hospital or the study center will not be recorded.

AEs that have not resolved before the initiation of administration in the extension study or at the end of follow-up must be followed-up until resolved or judged to be no longer clinically significant or until they become chronic to the extent that they can be fully characterized. If the event resolves during the study period, the date of resolution is to be entered in the eCRF.

See Appendix 4 “Liver Safety Monitoring and Assessment” for the assessment of AEs caused by DILI.

Herpes zoster should be entered as an AE information in the eCRF, and also, a separate Herpes Zoster (shingles) Worksheet should be prepared, and a copy should be submitted to the sponsor. If the sponsor considers necessary and requests for submission of forms for the purpose of providing additional information on other AEs, a form must be prepared to report to the sponsor.

5.4.3.1 Adverse Events of Possible Hepatic Origin

Subjects with liver-derived AEs associated with hepatic function abnormal should be monitored carefully.

5.4.4 Laboratory Assessments

The below hematology, biochemistry, fasting lipid profile, and urinalysis will be performed at screening and on each of the days specified in the Schedule of Assessments. These measurements will be performed at the central laboratory. For the period of performing additional laboratory tests for DILI, see Appendix 4 “Liver Safety Monitoring and Assessment.”

Additional sampling and tests may be performed if it is considered necessary by the investigator/sub-investigator or if retesting is considered necessary by the investigator/sub-investigator because the results could not be obtained due to defects in the sample. Additional tests and analysis may be performed based on the study results using blood samples for laboratory assessments that have been collected during the study and have been biobanked (i.e., residual samples stored for retrospective analyses).

- CONFIDENTIAL -

1) Hematology, biochemistry (including fasting lipid profile tests), urinalysis

The following hematology, biochemistry, fasting lipid profile tests, and urinalysis will be performed:

- Hematology

Hemoglobin, hematocrit, erythrocytes (RBC), leukocytes (WBC), differential WBC (neutrophils, lymphocytes, monocytes, eosinophils, basophils), platelet count

Each blood cell count will be calculated from the differential WBC.

- Biochemistry

Na, K, Ca, Cl, Mg, HCO₃, BUN, phosphorus, glucose, creatinine, ALP, AST (GOT), ALT (GPT), γ -GTP, total bilirubin, total protein, albumin, uric acid, CPK, LDH, serum amylase, eGFR, β -D-glucan

- Fasting lipid profile

Total cholesterol, LDL, HDL, triglycerides

The date of sample collection will be entered in the eCRF.

- Blood specimens for scheduled fasting lipid profile tests should be drawn after the subject has fasted for at least 8 hours, unless it is at termination or at an unscheduled visit when the subject could not fast.

- Urinalysis

pH, specific gravity, protein (qualitative), glucose (qualitative), keton bodies (qualitative), bilirubin (qualitative), occult blood, sediment

2) Pregnancy test (for females only)

Pregnancy testing will be performed from screening according to the Schedule of Assessments. Serum pregnancy testing is required only at screening, and urine pregnancy testing will be performed after baseline. The serum pregnancy testing will be performed by the central laboratory and the urine pregnancy testing will be performed by the study centers using the kits provided by the central laboratory. If, in the serum pregnancy test, hCG level exceeds ULN, but the possibility of pregnancy can be completely ruled out by another test, the subject is eligible for enrollment. Pregnancy testing is not subject to the safety assessment.

- If a urine pregnancy test is positive at any time, a negative serum pregnancy is required for the subject to continue participation in the study. If the possibility of pregnancy can be completely ruled out by another test, the subject may continue to participate in the study.
- The pregnancy tests need not be performed if the possibility of pregnancy can clearly be ruled out, such as if the woman is postmenopausal and has not had a menstrual period for 1 year or more, or has had a hysterectomy, bilateral oophorectomy, etc.

- CONFIDENTIAL -

3) Tuberculosis test

The tuberculosis test will be performed at screening to confirm the eligibility of the subject in accordance with Exclusion Criterion 14. T-SPOT or QuantiFERON Gold test is the preferential test for tuberculosis infection. If T-SPOT or QuantiFERON Gold test cannot be performed, tuberculin skin test may be performed instead. Tuberculin test and QuantiFERON Gold test cannot be performed at the central laboratory in Japan. Tuberculin test and T-SPOT cannot be performed at the central laboratory in Korea and Taiwan. Tuberculosis test is not required at screening provided that there is documentation of a negative tuberculosis test within 90 days prior to baseline.

4) Hepatitis test

Tests for HBs antigens, HBs antibodies, the HBV-DNA assay, HBc antibodies, and HCV antibodies will be performed at the screening visit to confirm the eligibility of the subject. If a subject is positive for either or both HBc antibodies and HBs antibodies, the subject will be monitored during treatment with the study drug or reference drug by performing an HBV-DNA assay at scheduled visits and early termination. Safety analysis will not be performed for the results of HBV-DNA assays from baseline.

5) CPK monitoring

If an increase in CPK is observed, in accordance with Section 5.4.4.1 CPK Monitoring, when CPK is retested, CPK, CK-MB, troponin T, and aldolase should also be tested. Urinalysis (blood and microscopy) will be performed as part of the targeted physical examination.

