Because ASP015K is an immunosuppressive agent, it may increase the risk of infections and reactivation of latent, chronic infections. In particular, excessive immunosuppression can lead to serious infections. Of note is the fact that Xeljanz[®] (tofacitinib) 5 mg, a member of the class of JAK inhibitors to which ASP015K belongs, has been associated with new onset or aggravation of serious infections such as tuberculosis, pneumonitis, sepsis, viral infections, and opportunistic infectious diseases including fungal infections. In addition, several cases of malignant tumors have been reported, although their causal relation to the agent has not been established. Based on the data pooled from 5 domestic and overseas comparative studies of Xeljanz[®] (tofacitinib) 5 mg, the incidence density of malignancies (excluding non-melanoma skin cancers) among RA patients treated with 5 mg BID for a maximum of 1 year was 0.55/100 person-years (incidence rate 0.5% < 5/1216) [Xeljanz[®] Pharmaceutical Interview Form (in Japanese)].

These findings suggest that investigators pay particular attention to the possible development of infections and malignancies and take appropriate measures. Three cases of malignancies (stomach cancer, uterine sarcoma, chronic myelogenous leukemia) have been reported as of the cut-off date of 5 December 2013, from completed and ongoing national and international studies of ASP015K. Only the case of uterine sarcoma was judged as related to ASP015K.

In the Japanese clinical trial in patients with moderate to severe RA (015K-CL-RAJ1), 50 mg and higher doses of ASP015K significantly improved the ACR20 response rate versus placebo. Xeljanz[®] (tofacitinib) 5 mg, which acts via the same mechanism as ASP015K, was approved by the US FDA in 2012 for the treatment of adult patients with moderate to severe RA who had an inadequate response to or are intolerant of MTX. In March 2013, Xeljanz[®] (tofacitinib) 5 mg tablets was authorized for marketing in Japan for treating RA patients who had an inadequate response to conventional therapies. Therefore, a potential benefit of JAK inhibitor ASP015K is to improve RA.

One can also expect that long-term use of ASP015K will improve QOL of RA patients by successfully controlling the RA disease activity over an extended period.

- CONFIDENTIAL -

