 - Hemoglobin < 9.0 g/dL
 - Absolute neutrophil count < 1000/ μ L
 - Absolute lymphocyte count < 800/ μ L
 - Platelet count < 75000/ μ L
 - ALT $\geq 2 \times$ ULN
 - AST $\geq 2 \times$ ULN
 - Total bilirubin (TBL) $\geq 1.5 \times$ ULN
 - Estimated GFR ≤ 40 mL/min as measured by the MDRD method
 - β -D-glucan > ULN [in case of Japan: ≥ 11 pg/mL]
 - Positive HBs antigen, HBc antibody, HBs antibody or HBV-DNA quantitation (However, subject with negative HBs antigen and HBV-DNA quantitation, and positive HBc antibody and/or HBs antibody is eligible if HBV-DNA is monitored by HBV-DNA quantitation at every scheduled visit after initiation of study drug or reference drug administration.)
 - Positive HCV antibody

- CONFIDENTIAL -

14. Subject has a history of or concurrent active tuberculosis (TB). Eligibility criteria for TB are tabulated below:

History of active TB	Chest x-ray (for TB)	TB infection ^{b)}	Exposure to patients with infective TB (interview)	Eligibility
Present	-	-	-	Not eligible
Absent	Abnormal (active)	-	-	Not eligible
	Abnormal (old) ^{a)}	-	Eligible	Eligible if prophylaxis is given ^{c)}
	Normal	Positive	Eligible	Eligible if prophylaxis is given ^{c)}
		Negative	Exposed	Eligible if prophylaxis is given ^{c)}
	Not exposed		Eligible	

a) Old TB is evidenced if chest x-ray reveals pleural thickening, band-like shadow, and calcification ≥ 5 mm. Chest x-ray within 90 days prior to baseline may substitute the screening test.

b) T-spot or Quantiferon Gold test is of first priority. When the result is equivocal or invalid, retest including other test methods may be allowed. If a retest is not performed, criteria for positive results will be followed. When T-spot or Quantiferon Gold test is not feasible, tuberculin test will be performed. Tuberculin is defined as positive with a red spot covering an area of 20 mm or more or induration. Tests conducted within 90 days prior to baseline may be used for diagnosis.

c) Subject must receive or have received prophylaxis with isoniazid or rifampicin. Prophylaxis will be administered for 6 to 9 months, starting from at least 21 days prior to baseline.

15. Subject meets any of the following in terms of infections except for TB:

- History of or concurrent severe herpes zoster (associated with Hunt syndrome or having ulcerative lesions) or disseminated herpes zoster
- History of multiple recurrences (at least twice) of localized herpes zoster

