3.4 Discontinuation Criteria for Individual Subjects

A discontinuation is a subject who enrolled in the study and for whom study treatment is permanently prematurely discontinued for any reason.

The subject is free to withdraw from the study treatment and/or study for any reason and at any time without giving reason for doing so and without penalty or prejudice. The investigator is also free to terminate a subject's involvement in the study at any time if the subject's clinical condition warrants it.

The Appendix 4 entitled "Liver Safety Monitoring and Assessment" describes liver function tests raised that provide grounds for discontinuation. Refer to Appendix 4 concerning the measures to take for increases in liver function test parameters.

The investigator/sub-investigator should discontinue the study if any of the following occurs:

1. The subject withdraws consent.
2. The investigator/sub-investigator judges that the study drug or reference drug is not sufficiently effective and the treatment method needs to be changed.
3. Symptomatic CPK elevation ($> 1.5 \times$ ULN accompanied with severe and unusual episodes of myalgia, muscular weakness, or muscle twitching).
4. Any case of myopathy involving severe and unusual episodes of myalgia, muscular weakness, or muscle twitching that persists for no less than, or aggravates rapidly within, 2 weeks, regardless of the CPK level.
5. A previously HBV-infected patient with positive HBe antibody, positive HBs antibody, or both has been shown positive for HBV-DNA during the study.
Attention should be paid that abrupt discontinuation of immunotherapy may cause fulminant or severe liver failure. Therefore, if the subject manifests HBV reactivation, the investigator/sub-investigator will administer nucleoside analogs without delay [unique to Japan: according to the "Proposal for Management of Rheumatic Disease Patients with Hepatitis B Virus Infection Receiving Immunosuppressive Therapy" (Japan College of Rheumatology)]. The investigator/sub-investigator will carefully decide whether to continue or discontinue the study drug, reference drug, and concomitant DMARDs in consultation with the hepatology specialist.
6. Malignant tumor

- CONFIDENTIAL -

7. The subject develops a serious infection or other AEs, and continued administration of the study drug is not deemed appropriate in the subject's best interest by the investigator/sub-investigator.

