5.5 Adverse Events and Other Safety Aspects

5.5.1 Definition of Adverse Events (AEs)

An AE is defined as any untoward medical occurrence in a subject administered a study drug or reference drug that does not necessarily have a causal relationship with this treatment. An AE can therefore be any unfavorable and unintended sign (including an abnormal laboratory finding), symptom, or disease temporally associated with the use of a study drug or reference drug, whether or not related to the study drug or reference drug.

- CONFIDENTIAL -

An abnormality identified during a medical test (e.g., laboratory parameter, vital sign, ECG data, physical examination) should be defined as an AE only if the abnormality meets one of the following criteria:

- Induces clinical signs or symptoms
- Requires active intervention
- Requires suspension, interruption, or discontinuation of the study drug or reference drug
- The abnormality or laboratory test value is clinically significant based on the opinion of the investigator or other responsible personnel

The particulars to be noted with respect to the AE are the name of the event, date of onset, date of disappearance, severity (at peak time), seriousness, treatment of the study drug or reference drug, other treatment, outcome, causal relationship to the study drug or reference drug, and rationale for the assessment of causal relationship. The rationale for the assessment of the causal relationship does not need to be recorded for all AEs but only at the request of the sponsor. The severity of each event should be recorded on a scale of Grade 1 to Grade 5 in the eCRF, and the causal relationship to the study drug should be recorded as “Probable,” “Possible,” or “Not related” (see Section 5.5.3 Criteria for Causal Relationship to the Study Drug and Section 5.5.4 Criteria for Defining the Severity of an Adverse Event). The treatment of the AE (whether it was treated with pharmacotherapy or by other means) and the treatment of the study drug or reference drug should be recorded in the medical record or other source documents and in the eCRF. The outcome should be recorded in the medical record or other source documents and in the eCRF as “resolved,” “alleviated,” “unresolved,” “resolved but with late effects,” “death,” or “unknown.”

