7.5.2 Clinical Laboratory Evaluation

All Laboratory Tests

For clinical laboratory parameters (hematology, biochemistry, fasting lipid profile, and urinalysis), raw values at each scheduled visit, change from baseline at each post-baseline visit, shift from baseline and shift from reference range will be summarized using descriptive statistics or frequency tabulations. No statistical hypothesis testing will be performed. For Fasting Lipids Profile, all analysis will be conducted using the measured values which are confirmed under fasting condition. In addition, all Lipid Profile values including non-fasting condition will also be summarized for descriptive statistics.

Clinical laboratory test is conducted at central institution at each region (Japan, Korea, Taiwan) in accordance with each procedure and each reagent for clinical test. The possibility of harmonization among each region was conducted before clinical laboratory test was initiated in Korea and Taiwan. If clinical laboratory evaluation could be harmonized, then these measurement data among each region could be regarded as the same scale. If harmonization was reported to be difficult, then clinical test would be summarized by Study Region (Japan, Korea, Taiwan). However, among clinical laboratory tests not-harmonized, for exploratory analysis, Beta-D-glucan, Glucose, HCO₃, urine pH, urine gravity will be summarized by whole population. Qualitative Urinalysis test will be summarized by Study Region, only (see 7.8.2 Subgroup analysis for Study Region (Japan, Korea, Taiwan)).

- Clinical laboratory tests harmonized
 - All of the hematology test
 - Biochemistry test except for Beta-D-glucan, Glucose, HCO₃
 - All of the fasting lipid profile
 - CRP
 - Clinical laboratory tests not-harmonized
 - Beta-D-glucan, Glucose, HCO₃
 - All of the urinalysis test
- * For Beta-D-glucan, reference range is not validated throughout the study period and it will be displayed in listing only.
- * Pregnancy test, CPK monitoring, Hepatitis test, Hepatitis DNA test are not applicable to harmonization and it will be displayed in listing only.
- For continuous variables, descriptive statistics of raw values at each scheduled visit will be summarized at each time point using SI unit. For the ratio T-Chol to HDL and the ratio LDL to HDL, descriptive statistics will be summarized at each post-baseline visit.

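### No planned summary table gives the number of HBV-antibody-positive subjects monitored, or the incidence of HBV-DNA positivity among them

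*Protocol*

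**What the plan says.** The plan sets up HBV surveillance in four places.

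- **Risk.** Protocol 1.4 describes ASP015K as immunosuppressive and says "it may increase the risk of infections and reactivation of latent, chronic infections".
- **Entry.** Under Protocol 3.3, criterion 13, a subject who is negative for HBs antigen and HBV-DNA but positive for HBc and/or HBs antibody "is eligible if HBV-DNA is monitored by HBV-DNA quantitation at every scheduled visit after initiation of study drug or reference drug administration". Appendix 2 of the protocol gives the visits: baseline and every four weeks from Week 4 to Week 52.
- **Action.** Protocol 3.4, criterion 5, lists as a ground for discontinuation that a previously infected subject "has been shown positive for HBV-DNA during the study". If the virus reactivates, the investigator "will administer nucleoside analogs without delay" and decides with a hepatologist whether study treatment continues.
- **Reporting.** Protocol 5.4.4, under the hepatitis test, says "Safety analysis will not be performed for the results of HBV-DNA assays from baseline". SAP 7.5.2 says "Pregnancy test, CPK monitoring, Hepatitis test, Hepatitis DNA test are not applicable to harmonization and it will be displayed in listing only".

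**The concern.** The trial requires repeated testing in a defined group because of a risk it names, and then sets a rule that the results will not be summarised. The protocol and SAP do not conflict; this is a stated choice. Its consequence is that no planned table identifies the group at risk.

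A reader of the study report could see how many conversions were recorded as adverse events in each arm. The tables would not say how many subjects were being followed for that event, what proportion of them converted on ASP015K or etanercept, or how much a count of zero rules out.

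**Working it through.** **Step 1. Look for the denominator in the planned tables.** I looked for any summary that counts antibody-positive subjects or divides by them.

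| Planned output | Antibody status or HBV-DNA used? |
|---|---|
| SAP 7.2.2, Tables 5 and 6 (demographics, RA history) | No |
| SAP 7.2.2.4, medical history | Only if a site recorded it as a diagnosis |
| SAP 7.5.2, Table 7 (selected laboratory variables) | No |
| SAP 7.5.2.1, liver abnormalities | No; ALT, AST, ALP and bilirubin only |
| SAP 7.8.1, subgroups | No |
| SAP Appendices 3 and 4 (AE and laboratory overviews) | No |
| SAP Appendix 8, AEs of special interest | No HBV category |
| SAP Appendix 9, CTCAE grading | No |
| Listing under SAP 7.5.2 | Yes, subject by subject |

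The listing is the only planned output that holds both pieces of information.

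**Step 2. Trace where a conversion would otherwise appear.** Protocol 5.5.1 makes an abnormal test an adverse event if, among other conditions, it needs active intervention or "Requires suspension, interruption, or discontinuation of the study drug or reference drug". A conversion treated with an antiviral, or leading to interruption, meets that rule. It then enters the adverse event tables and, where applicable, the tables of events leading to discontinuation. If serious and coded to the infections class, it enters Serious Infections, which has rates per 100 patient-years with a 95% CI (SAP 7.5.1.2). Liver enzyme consequences appear in SAP 7.5.2.1. The incidence tables are based on the safety analysis set, which is everyone dosed (SAP 5.3), so their percentages include subjects not monitored for HBV-DNA.

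**Step 3. Illustrate the effect of the denominator.** The plan states no figure to reproduce.

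- From Protocol 7.1: 100 subjects per study-drug arm and 200 on etanercept.
- Assumption: an antibody-positive share of 10%, 20% or 30%. The documents give none.
- Number monitored n = arm size × share.
- Intervals are Clopper-Pearson 95%. With zero events the upper limit is 1 − 0.025^(1/n).

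| Arm | Share | n | One event, of all dosed | One event, of n (95% CI) | Zero events, upper limit |
|---|---|---|---|---|---|
| ASP015K, 100 | 10% | 10 | 1.0% | 10.0% (0.3 to 44.5) | 30.8% |
| ASP015K, 100 | 20% | 20 | 1.0% | 5.0% (0.1 to 24.9) | 16.8% |
| ASP015K, 100 | 30% | 30 | 1.0% | 3.3% (0.1 to 17.2) | 11.6% |
| Etanercept, 200 | 10% | 20 | 0.5% | 5.0% (0.1 to 24.9) | 16.8% |
| Etanercept, 200 | 20% | 40 | 0.5% | 2.5% (0.1 to 13.2) | 8.8% |
| Etanercept, 200 | 30% | 60 | 0.5% | 1.7% (<0.1 to 8.9) | 6.0% |

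If a reader applied zero events to the whole arm of 100, the upper limit would be 1 − 0.025^(1/100) = 3.6%. The limit among those monitored is about 3 times (11.6/3.6) to 8.5 times (30.8/3.6) larger.

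Pooling helps. If all 100 placebo subjects switched, up to 300 would receive ASP015K, so 30 to 90 would be monitored, and the zero-event upper limit would be 11.6% to 4.0%.

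**The case against.** The strongest reply is that the plan already covers what matters. The listing is a planned output, and both counts can be made from it. Managed, serious or discontinuing cases reach by-arm tables through the routes in Step 2. HBV-DNA is there to manage individual subjects. Pregnancy tests and CPK-monitoring tests are handled in the same way. The resulting percentages would rest on few subjects, with wide intervals and an unknown share at risk, and antibody-positive subjects may not all carry the same risk.

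Most of this stands. It limits the point to a missing tabulation; it does not show lost information or unreported harm. It does not supply the denominator, and small numbers are a reason to show it. Evaluating the safety of ASP015K is a stated objective (Protocol 2.1).

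Four stronger readings are tempting and are not supported:

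- **That no planned output carries the data, or that reactivations would go unseen.** The listing carries the data, and most managed conversions meet the adverse event definition.
- **That the protocol already defines a positive result.** Protocol 3.4 gives no quantitation cut-off and no confirmation rule. SAP 7.11.1 has no rule for HBV-DNA below the limit of quantification.
- **That the assays failed harmonisation, so results must be shown by region.** The SAP rule reads "If harmonization was reported to be difficult, then clinical test would be summarized by Study Region (Japan, Korea, Taiwan)". The tests it lists as not harmonised are beta-D-glucan, glucose, HCO3 and urinalysis. HBV-DNA is described as outside harmonisation, which is a different statement.
- **That a protocol amendment is needed.** SAP section 1 lets changes from planned analyses be justified in the CSR.

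**Conclusion.** The concern holds as a reporting gap. No planned summary table gives the number of HBc- or HBs-antibody-positive subjects monitored, or the incidence of HBV-DNA positivity among them, and the adverse event tables use all dosed subjects as denominator.

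The size depends on the antibody-positive share, which the documents do not give. At an assumed 10% to 30%, one conversion in an ASP015K arm would be 10.0% to 3.3% of those monitored, against 1.0% as tabulated. These figures illustrate the scale and predict nothing about the trial.

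The primary analysis, the between-arm comparison and individual monitoring are unaffected. The change is worth making because it is cheap and serves the trial's own safety objective.

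**What to change.** In SAP 7.5.2, replace the listing-only rule for HBV-DNA with one descriptive table and keep the listing. The table should give:

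- the number of antibody-positive subjects with at least one post-baseline HBV-DNA result, with HBc-positive shown separately from HBs-antibody-only;
- the number and percentage with any post-baseline result that the laboratory reported as positive, with an exact 95% CI and no testing;
- a footnote stating the cut-off for positive and how results detected but below quantification are handled.

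Present it by initial arm for Weeks 0 to 12, and by treatment sequence plus ASP015K Total overall. The existing Week 12 rules (SAP 6.2 and 7.11.6) can assign results around the switch. A footnote should say that switched subjects have about 52 − 12 = 40 weeks on ASP015K.

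Record the departure from the Protocol 5.4.4 sentence in the SAP and CSR. The cost is one SAP revision, ideally before unblinding, and one table from data already collected, with no extra tests. The downside is small counts and wide intervals.
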